3.2.3 Analysis Visit Summarization

All primary and secondary efficacy endpoints except vital signs, leptin/adiponectin and ALT/AST will be mapped by analysis visit and record selection rules, as specified in Appendix A. For display and analyses purposes, the assessments will be displayed by the scheduled visits as described in the protocol and will use the analysis visit algorithm where necessary. Other safety assessments will be summarized by the nominal visit as collected in the data and will not use visit analysis window mapping.

Summary table over time (visits) for non-efficacy endpoints will average all records within each nominal visit.

3.2.4 Patient Populations Analyzed

The following analysis sets will be used for the analysis of data as described within each analysis set.

Screened Patients is defined as those patients who signed an informed consent form.

Randomized Patients is defined as those screened patients who received a randomization assignment.

Safety Set (SS): All patients who are randomized and received at least 1 dose of Study Drug (ISIS 703802 or placebo). This population will be used for all safety analyses.

Full Analysis Set (FAS): All patients who are randomized and received at least 1 dose of Study Drug. The FAS represents the practically-feasible intent-to-treat (ITT) population as delineated in ICH Guideline E9. This population will be used for the analysis of efficacy.

Per Protocol Set (PPS): A subset of the FAS who have received within 6 months at least 22 weekly doses of Study Drug for patients randomized to Cohort A and at least 5 monthly doses of Study Drug for patients randomized to Cohorts B and C, and who have reported no major protocol deviations that

could compromise the interpretation of efficacy. Major deviations will be determined prior to unblinding for statistical analysis. This population will be used for supportive inferences concerning efficacy.

PK Population: All patients who are randomized and received at least 1 dose of ISIS 703802, and have at least 1 evaluable concentration result post first dose. This population will be used for analysis of PK data.

PK Subgroup: A subset of PK population who will have additional blood draws after dose administration on Day 1 and Week 26 (Cohort A) / Week 21 (Cohort B & C) to evaluate pharmacokinetic parameters.

3.2.5 *Sample Size Considerations*

Patients in the placebo arm will be pooled for the statistical analysis in order to compare each active treatment to the pooled control group. Therefore, each of the 4 treatment groups will have approximately 24 patients. Considering 10% dropouts, approximately 21 patients per group are expected to complete the study.

A sample size of 21 patients per arm will be able to detect:

- A treatment difference in mean triglycerides of 50% based on a between-patient standard deviation of 46% (Jani et al. 2014) and a two-sample t-test with an unadjusted alpha level of 0.05 with 93% power.
- A treatment difference in mean liver fat of 4.75% based on a between-patient standard deviation of 3.96% (Tiikkainen et al. 2004) and a two-sample t-test with an unadjusted alpha level of 0.05 with 96% power.

A total of approximately 96 patients (32 patients per cohort, including 24 patients per cohort treated with ISIS 703802) will be randomized to ensure that the efficacy of ISIS 703802 will be adequately characterized in the study.

3.2.6 *Baseline and Endpoint Definition*

For baseline platelet counts, all assessments from central and local labs will be used. For all other lab data, only values obtained from the central or reference lab will be used for baseline definition.

Baseline for triglycerides, ANGPTL3, TC, LDL-C, HDL-C, VLDL-C, Non-HDL-C, ApoB (ApoB-48, ApoB-100), ApoC-III, ApoA-I, FFA, Lp(a), and other lipid measurements is defined as the average of Day 1 pre-dose assessment and the last non-missing measurement prior to Day 1 pre-dose assessment. If 1 of the 2 measurements is missing, then the other measurement will be assigned as the baseline value. If both are missing, then the baseline will be set as missing. Note that if on Day 1, there are multiple pre-dose assessments, then the last assessment with non-missing value will be used as the Day 1 pre-dose assessment.

Baseline for platelets is defined as the average of all central and local lab assessments combined prior to the first administration of Study Drug.

Baseline for ALT and AST is defined as the average of Day 1 pre-dose assessment and the last non-missing measurement prior to Day 1 pre-dose assessment.

Baseline for ECG is the average of the three ECG assessments taken on Day 1 Pre-dose for ECG. If only one or two ECG assessments are available, the single ECG assessment or average of the two ECG assessments will be used. If Day 1 Pre-dose ECG is missing, the averages of the ECGs obtained during the screening visit will be used as baseline.

Baseline for other measurements are defined as the last non-missing assessment prior to the first administration of Study Drug.

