## 10.4 Definition of Baseline

Baseline for TG, ANGPTL3, TC, LDL-C, HDL-C, VLDL-C, Non-HDL-C, ApoB (ApoB-48, ApoB-100), ApoCIII, ApoAI, FFA, Lp(a), and other lipid measurements will be defined as the average of Day 1 pre-dose assessment and the last measurement prior to Day 1 pre-dose assessment. The Baseline for other measurements is defined as the last non-missing assessment prior to the first dose of Study Drug.

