**Appendix A Schedule of Procedures – Weekly Dosing *Continued***

Study Week	Screening r		Treatment Period												Follow-up Period			
	Run-in #	Qual *	1	1	5	9	13	17	21	25	26			27/ET	4*	8*	13*	
Study Day	-5 to -1	-1 to 0	1	2 a	29	57	85	113	141	169	176	177 a	178 a	183	* Weeks from the end of treatment period q			
Visit and Testing Window +/- Days	0	0	0	0	2	2	2	3	3	3	3	0	0	3	3	3	3	
Liver Biomarkers			X				X		X					X			X	
Plasma PK - ISIS 703802 l			X 	X 	X	X	X	X	X		X 	X 	X 	X	X	X	X	
Anti-ISIS 703802 Antibodies			X		X	X	X		X					X	X		X	
FSH (women only, if applicable) j, m	X																	
Serum Pregnancy Test m	X		X		X	X	X	X	X	X				X	X	X	X	
Archived Serum & Plasma Samples j, n			X			X		X	X					X	X	X	X	
PD Panel and phospholipids j	X	X	X		X	X	X	X	X		X			X	X	X	X	
Extended Lipid Panel j	X	X	X		X	X	X	X	X		X			X	X	X	X	
HbA1C j	X		X				X							X			X	
FPG, and delipidated free glycerol, insulin j	X		X		X	X	X	X	X		X			X	X	X	X	
Biomarkers of Inflammation			X				X							X			X	
Study Drug: SC Injection			EVERY WEEK SUBCUTANEOUS ADMINISTRATION OF STUDY DRUG (Week 1 through Week 26/Day 176) o															
Adverse Events	X		X	X	X	X	X	X	X	X	X	X	X	X	X	X	X	X
Concomitant Medication	X		X	X	X	X	X	X	X	X	X	X	X	X	X	X	X	X

† Qual =Qualification

# Subjects on stable diet known to the investigator and followed at the site may go from Screening to qualification without the diet run-in period.

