3.3 Efficacy Analyses

Table 3 specifies efficacy analyses types, endpoint, population, statistical model and whether log-transformed data and multiple imputation are needed.

Table 3: Summary of Analysis Methods in Efficacy Analyses for Continuous Efficacy Endpoints

| Endpoint | Analysis Type | Log-Transformed Data | MCMC imputation | Population | Model |
|------------------|------------------------|----------------------|--|------------|---------------------------------------|
| Primary Endpoint | Primary analysis | Yes | Yes, assume MAR | FAS | ANCOVA |
| | Sensitivity Analysis 1 | Yes | Yes, assume MAR | PPS | ANCOVA |
| | Sensitivity Analysis 2 | Yes | Yes, assume MAR | FAS | non-parametric Wilcoxon Rank Sum test |
| | Sensitivity Analysis 3 | Yes | Yes, assume MAR | PPS | non-parametric Wilcoxon Rank Sum test |
| | Sensitivity Analysis 4 | Yes | Yes, Placebo: assume MAR. ISIS Treatment group: | FAS | ANCOVA |

| | | | | | |
|---|--------------------------|--|--|-------------|--------|
| | | | Missing before discontinuation, assume MAR missing after discontinuation assume CIR | | |
| | Sensitivity Analysis 5 | Yes | No | FAS | ANCOVA |
| | Sensitivity Analysis 6 | Yes | No | FAS | MMRM |
| | Subgroup analysis | Yes | Yes | FAS | ANCOVA |
| Secondary Endpoints: ANGPTL3 protein, TC, LDL-C, HDL-C, VLDL-C, Non-HDL-C, ApoB (ApoB-48, ApoB-100), ApoC-III, ApoA-I, FFA, Lp(a) | Secondary analysis | Yes for Percent change from baseline; No for change from baseline | No | FAS and PPS | ANCOVA |
| Other Secondary Endpoints | Secondary analysis | No | No | FAS and PPS | ANCOVA |
| ██████████ ██████████ | ██████████ ██████████ | ██████████ ██████████ ██████████ ██████████ | No | FAS | ANCOVA |
| LDL-C | Subgroup analysis | Yes for Percent change from baseline; No for change from baseline | No | FAS | ANCOVA |

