3.3.1.2 Primary Efficacy Analysis

The percent change from baseline in triglycerides will be analyzed using an ANCOVA model with treatment group as a fixed factor and log-transformed baseline triglycerides as a covariate. The ANCOVA model will use $\log(Y/\text{base})$ as dependent variable, where Y is the post-baseline value of triglycerides and base is the baseline value of the triglyceride. The model will provide an estimate of the log ratio, which will then be converted back to the original ratio scale. The percent change from baseline will then be estimated based on the estimated ratio. Patients with missing primary endpoint will have their fasting triglyceride value imputed using the following multiple imputation method described below.

Missing data for the primary efficacy endpoint will be handled by a multiple imputation model that contains the following variables: log-transformed baseline fasting triglyceride value, log-transformed fasting post-baseline triglyceride values, stratified by treatment (Schafer 1997; Schafer 1999). Imputation of missing data will be conducted under a working assumption of missing at random (MAR), meaning that the propensity for a data point to be missing is not related to the missing data, but it is related to some of the observed data.

The imputations will be performed for post-baseline visits. The Markov Chain Monte Carlo (MCMC) method will be used under the multivariate normality assumption to impute the missing primary endpoint by treatment group (ISIS 703802 treatment group or pooled placebo treatment group). In order to be compliant with the normality assumption, baseline and post-baseline triglyceride data will be log-transformed prior to the imputation process. Jeffreys' prior will be used to derive the posterior distribution of the parameters. The MCMC method will impute 100 datasets in order to estimate the treatment effect.

The primary endpoint will be compared between each ISIS 703802 treatment group and the pooled placebo group for each of the 100 imputed datasets. The estimates from the 100 fitted models will be combined to provide an overall estimate, with corresponding CIs and p-value ([Little and Rubin, 2002](#)). Results from the ANCOVA model will be tabulated by ISIS 703802 treatment groups compared to the pooled placebo group.

For fasting triglycerides, all observed values, change from baseline and percentage of change will be summarized by analysis visit using descriptive statistics in FAS.

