3.3.2 Secondary Efficacy Analyses

All analyses of secondary endpoints will be performed on the FAS as primary and the PPS as supportive. Secondary efficacy analyses will be based on data collected at the primary analysis time point.

- Change and percent change from baseline at the primary analysis time point in ANGPTL3 protein, TC, LDL-C, HDL-C, VLDL-C, Non-HDL-C, ApoB (ApoB-48, ApoB-100), ApoC-III, ApoA-I, FFA, Lp(a) will be compared between each ISIS 703802 group and pooled placebo group using an ANCOVA model without applying any imputation for missing data. In ANCOVA model, $\log(Y/X)$ will be dependent variable, where Y is the post-baseline lipid value and X is the baseline lipid value, log-transformed baseline will be a covariate.
- Change from baseline at the primary analysis time point in fasting plasma glucose, HbA1c, fasting insulin, HOMA-IR, fructosamine and glycated albumin will be compared between each ISIS 703802 treatment group and pooled placebo group using an ANCOVA model with baseline as covariate.
- Change and percent change from baseline at the primary analysis time point in weight, SBP and DBP will be compared between each ISIS 703802 treatment group and pooled placebo group using an ANCOVA model with baseline as covariate.
- Change and percent change from baseline at the primary analysis time point in hepatic fat fraction (HFF) by MRI-PDF will be compared between each ISIS 703802 treatment group and pooled placebo group using an ANCOVA model with baseline as covariate.

- Proportion of patients reaching hepatic fat fraction (HFF) $\leq 8\%$ and $< 5\%$ by MRI-PDFF at the primary analysis time point will be compared between each ISIS 703802 treatment group and pooled placebo group using a logistic regression model with baseline HFF as a covariate.
- Proportion of patients with percent decrease from baseline in hepatic fat fraction (HFF) by MRI-PDFF $\geq 30\%$ and $\geq 25\%$ at the primary analysis time point will be compared between each ISIS 703802 treatment group and pooled placebo group using a logistic regression model with baseline HFF as a covariate.
- Change from baseline at the primary analysis time point in Fatty Liver Index (FLI) will be compared between each ISIS 703802 treatment group and pooled placebo group using an ANCOVA model with baseline as covariate. Equation below will be used for FLI calculation:

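### Five glycaemic markers get a single-value baseline although a second fasted pre-dose sample is scheduled and the SAP already averages two for lipids, ANGPTL3, ALT and AST: a modest, avoidable loss of precision

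*SAP*

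**What the plan says.** **Baseline.** SAP 3.2.6 gives lipids and ANGPTL3 a baseline that "is defined as the average of Day 1 pre-dose assessment and the last non-missing measurement prior to Day 1 pre-dose assessment", and applies the same rule to ALT and AST. Platelets and ECG have rules of their own. Everything else, including the five glycaemic markers, falls under "Baseline for other measurements are defined as the last non-missing assessment prior to the first administration of Study Drug". Protocol 10.4 agrees: "The Baseline for other measurements is defined as the last non-missing assessment prior to the first dose of Study Drug". It restricts averaging to lipids and ANGPTL3; ALT and AST are an SAP addition.

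**Analysis.** SAP 3.3.2 covers "Change from baseline at the primary analysis time point in fasting plasma glucose, HbA1c, fasting insulin, HOMA-IR, fructosamine and glycated albumin", each by ANCOVA with baseline as covariate. SAP Table 3 has the row "Other Secondary Endpoints | Secondary analysis | No | No | FAS and PPS | ANCOVA", where the two entries of No mean no log transformation and no imputation. Protocol 10.1.2 also defines these endpoints as absolute change.

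**Samples.** In Protocol Appendix A, both schedules mark the row "PD Panel and phospholipids" at Screening, Qualification and Day 1, with a footnote requiring an overnight fast. Appendix B places insulin, fasting glucose, fructosamine and glycated albumin in that panel. SAP Appendix A lists HOMA-IR with the PD parameters and gives them a Qualification window of Day -7 to before Day 1.

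**The concern.** A second fasted pre-dose value is scheduled within about a week of Day 1 and is left out of the baseline. A single insulin or glucose reading carries day-to-day noise, and a noisy covariate removes less between-patient variation in ANCOVA. The SAP accepts this reasoning for lipids and gives no reason for stopping short of the glycaemic markers.

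Glucose metabolism is a named secondary objective (Protocol 1.2, SAP 1.2.2). SAP 1.3 hypothesises better glycaemic control, including less insulin resistance. With about 21 completers per group and no power stated for these markers, precision already paid for is worth keeping. A second question is whether insulin and HOMA-IR, if right-skewed, should be modelled only as untransformed change.

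**Working it through.** **1. The plan's own power figures.** With 21 per group and a two-sided 0.05 t-test (noncentral t):
- triglycerides: 50/46 = 1.087 SD, power 93.0% (stated 93%);
- liver fat: 4.75/3.96 = 1.199 SD, power 96.7% (stated 96%).

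Both reproduce. There is no corresponding figure, SD or effect size for any glycaemic marker, so everything below rests on assumed inputs.

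**2. Residual variance with one or two baselines.** Let rb be the correlation between the two pre-dose values and rf the correlation of each with Week 25/27. All visits have unit variance.
- One baseline: 1 − rf².
- Mean of two: the mean has variance (1 + rb)/2 and covariance rf with the outcome, so the residual is 1 − 2rf²/(1 + rb).

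With baseline as covariate, the treatment contrast is the same for change as for the final value, so these formulas apply to the planned analysis.

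**3. Conversion to power.** At 21 per group, 80% power needs a standardised difference of 0.886. Dividing it by the square root of the variance ratio gives the power with two baselines.

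| rb / rf (assumed) | One | Mean of two | Ratio | 80% becomes |
|---|---|---|---|---|
| 0.5 / 0.5 | 0.750 | 0.667 | 0.889 | 84.4% |
| 0.6 / 0.6 | 0.640 | 0.550 | 0.859 | 85.6% |
| 0.7 / 0.7 | 0.510 | 0.424 | 0.830 | 86.7% |
| 0.8 / 0.8 | 0.360 | 0.289 | 0.802 | 87.8% |
| 0.7 / 0.5 | 0.750 | 0.706 | 0.941 | 82.3% |
| 0.8 / 0.6 | 0.640 | 0.600 | 0.938 | 82.5% |
| 0.9 / 0.6 | 0.640 | 0.621 | 0.970 | 81.2% |
| 0.9 / 0.8 | 0.360 | 0.326 | 0.906 | 83.7% |

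Equal correlations give an 11% to 20% reduction. The three cases with pre-post correlation 0.5 or 0.6 and a higher pre-pre correlation give 3% to 6%, and 0.9/0.8 lies between at 9%. The closed form gives a gain of about 1 to 8 points at 80% power. Simulations with skewed data put it at about 2 to 9.

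**4. Adding a log scale for insulin and HOMA-IR.** The simulation used four groups of 21, lognormal data, a 25% fall in all three active groups, and ANCOVA with group and baseline. Power for one active group against placebo:

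| Log-SD; rb / rf (assumed) | As planned | Both changes |
|---|---|---|
| 0.7; 0.75 / 0.75 | 42% | 59% |
| 0.5; 0.6 / 0.6 | 60% | 69% |
| 0.7; 0.9 / 0.75 | 43% | 53% |
| 0.5; 0.8 / 0.6 | 61% | 65% |

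In the first row, two baselines alone give 49% and log-ratio alone 50%; in the second, 66% and 63%. Repeat runs move these figures by a point or two (the last row's gain was 4 in one run and 6 in another), so both changes together add about 5 to 17 points. Type I error stays near 5%.

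**5. Fasting glucose.** In a two-group simulation with an assumed CV of 20% and power near 80%, log transformation alone adds about 1 point (for example 78.0% to 79.3%). The second baseline adds about 3 to 7 (77.7% to 80.5%; 78.4% to 85.1%).

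**The case against.** The strongest reply is that nothing here is wrong. Protocol and SAP agree on the baseline rule, the test is valid, no power is promised, and dose selection rests on triglycerides and safety. All of that stands, and it limits the point to efficiency.

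Other objections also have force:
- **The baseline gain may be small.** The pre-dose samples are days to weeks apart while the endpoint is about six months later, so a higher pre-pre than pre-post correlation is plausible. The low end of the range has to be shown.
- **The schedule is not fully clear.** A separate row for fasting glucose and insulin shows Screening and Day 1 but not Qualification. If Screening supplied the earlier value, it could precede the four-week diet run-in. The PD panel row and the SAP's Qualification window answer this in the normal case.
- **The ALT/AST precedent is imperfect.** Protocol 8.5 and 8.6 already use an averaged baseline for safety rules, which may explain it. The lipid precedent is unaffected.

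A reader might infer more than the documents support:
- **That power loss is substantial.** Gains from 32% to 59% and from 50% to 70% appear in the simulation of step 4 only if one active group works and the other two equal placebo. Protocol 2.4 predicts triglyceride falls of about 45% to 55% across the regimens. When all active groups respond, the pooled raw-scale variance shrinks and the planned analysis does better. A model with only two groups also shows larger losses, but the SAP's sample ANCOVA code keeps all four groups together.
- **That log-ratio should replace the planned model.** The protocol endpoint is absolute change. Table 3 logs lipids for percent change only, so raw modelling of absolute change is consistent with it. Lognormal data with a multiplicative effect also favour the log model by construction.
- **That insulin resistance is a separate objective.** It sits within glucose metabolism, which HbA1c also serves.

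**Conclusion.** The point holds as a modest efficiency loss. Five markers are given one pre-dose value where a second fasted value is scheduled, while the SAP averages two elsewhere. Averaging would lower residual variance by about 11% to 20% under equal visit correlations of 0.5 to 0.8. Where the pre-dose values are more alike to each other than to Week 25/27, the reduction is about 3% to 6%. That is roughly 2 to 9 power points, and close to 1 in the least favourable closed-form case.

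The further benefit of a log scale applies only to insulin and HOMA-IR and only if they are skewed, which the documents do not establish. With an assumed log-SD of 0.5 to 0.7 and all active groups effective, both changes add about 5 to 17 points for a 25% fall. A substantial loss is not shown for fasting glucose. No conclusion of the trial becomes invalid if the plan stays as written.

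**What to change.** - **SAP 3.2.6:** define baseline for fasting insulin, HOMA-IR, fasting glucose, fructosamine and glycated albumin as the mean of the Day 1 pre-dose value and the last non-missing earlier value, normally Qualification (Day -7 to -1), as for lipids. Carry over the lipid rule for one missing value. Confirm that the PD panel row governs sampling at Qualification.
- **Endpoint:** keep absolute change by ANCOVA as the protocol-defined analysis, and record in the SAP that this baseline departs from Protocol 10.4. HbA1c stays as it is, since it is not drawn at Qualification.
- **Optional, before unblinding:** add to Table 3 and 3.3.2 a supportive ANCOVA of log(Y/base) on group and log(base) for insulin and HOMA-IR, reported as percent change beside the absolute-change result and not in place of it.

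The cost is a minor documented deviation from the protocol's baseline wording and, if the option is taken, one extra analysis. No new samples or visits are needed.

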3.2.7 Patient Characteristics

Disposition and Protocol Deviations

Patient disposition, including reasons for premature discontinuation of treatment or follow-up, number of patients in Randomized Patients, SS, FAS, PPS, PK Population, and PK subgroup will be summarized for all screened patients. Listing of patient disposition will also be provided for Randomized Patients.

Major protocol deviations will be summarized by deviation category for Randomized Patients. All protocol deviations (major and minor) will be listed for Randomized Patients. Reasons for excluding patients from Per-Protocol Set will be summarized.

Demography and Baseline Characteristics

Patient demographic characteristics, including age (in years), sex, race, ethnicity will be summarized by treatment group for the FAS.

Baseline characteristics will include: weight (in kg) and weight by sex, height (in cm), BMI and BMI by sex, WHR, history of hepatic steatosis and years since diagnosis, history of confirmed type 2 diabetes mellitus and years since diagnosis, triglycerides, ANGPTL3, TC, LDL-C, HDL-C, VLDL-C, Non-HDL-C, ApoB (ApoB-48, ApoB-100), ApoC-III, ApoA-I, FFA, Lp(a), HbA1c, HFF, VAT, SAT, biomarkers of inflammation (IL-6, TNF-a, IFN-g) and adipokines (as available), and will be summarized by treatment group for the FAS.

Previous medical history will be summarized by treatment group for the FAS.

Medication

All medications will be coded by World Health Organization Drug Dictionary (WHODrug, Version DEC2017). Missing or partial dates will be imputed as outlined below under conservative principles.

Missing or partial start dates:

- If year, month and day are all missing then assign the date of first administration of Study Drug
- If month and day are missing and year is:
 - earlier than the year of the first administration of Study Drug then assign December 31
 - otherwise, assign January 1
- If only day is missing and month-year is:

- earlier than the month-year of the first administration of Study Drug then assign the last day of the month
- otherwise, assign the first day of the month

Imputation will be performed for the end date only if the day or month is missing (i.e., year is present) for a stopped prior/concomitant medication as follows:

- If month and day are missing then assign December 31
- If only day is missing then assign the last day of the month

If the imputed start date is later than the imputed end date then set the imputed start date to the imputed end date.

Imputed start and stop dates will be used to determine whether the medications are prior or concomitant to the treatment period. Prior medications include medications administered between the date of signed the informed consent and the first dose date, regardless whether continued while on treatment or not. A concomitant therapy is any drug or substance (including over-the-counter (OTC) medications, herbal medications and vitamin supplements) administered between first administration of Study Drug and patient’s last contact date within the study. A prior medication with an imputed stop date that is missing or on or after date of first administration of Study Drug will also be considered as a concomitant medication. Medications will be classified based on (imputed) start and (imputed) stop dates as follows:

1) Prior Medication

| Start Date | End Date |
|-------------------|-----------------------|
| < FDD | ≥ Inform Consent Date |
| | Missing |

FDD = Date of First Dose of Study Drug

2) Concomitant Medication

| Start Date | End Date |
|-------------------|---------------------------|
| < FDD | ≥ FDD |
| | Missing |
| ≥ FDD | Any non-missing stop date |
| | Missing |

FDD = Date of First Dose of Study Drug

Medication verbatim terms will be coded to Anatomical Therapeutic Chemical (ATC) classification and preferred name using the World Health Organization Drug Dictionary (Version DEC2017).

Prior and concomitant medications will be summarized separately by ATC class, preferred term, treatment group with counts and percentages, sorting by decreasing frequency in the All Patients

column. The concomitant medications in on-treatment and on-study period will be summarized respectively.

Prior and concomitant medications will be displayed in patient listings for all randomized patients. Note that imputed dates will be used for prior and concomitant medications classification. Original reported dates will be used for listings.

Treatment Exposure and Compliance

Treatment duration and amount of Study Drug received will be summarized by treatment group and overall in Safety Set. Compliance to Study Drug will be summarized by descriptive statistics by treatment group and overall.

Treatment exposure in days will be calculated as date of last dose minus date of first dose +1 day.

Compliance (%) will be calculated as follows:

$$100 \times (\text{total volume of Study Drug}) / (\text{total volume of Study Drug scheduled during the treatment period}).$$

For early withdrawals/terminations, the volume of Study Drug will be calculated for the period up to their withdrawal/termination.

